6.9 Pharmacokinetic Analysis

PK Data Reporting and BLQ Imputation:

Individual plasma concentration data will be listed and summarized by cohort and dose levels / nominal time point with descriptive statistics (sample size [N], arithmetic mean, standard deviation [SD], median, minimum, maximum, geometric mean, and percent coefficient of variation [CV%]). Only concentration data collected within window of the scheduled timepoint will be included in summary tables and figures, however all data will be provided in data listings. Individual concentration data and descriptive statistics will be presented to 3 significant figures, except N, which will be reported as whole number CV% will be reported to one decimal place. For the purpose of descriptive statistics on the plasma concentration values and for PK analysis, all non-numerical values reported as being below the lower limit of quantification (BLQ) will be imputed as follows:

- Any BLQ value will be presented as 'BLQ' in the concentration table listings and footnoted accordingly.
- Any BLQ value prior to C_{max} will be set equal to zero. Any BLQ post C_{max} will be kept as "BLQ" and treated as a non-numerical value and excluded from descriptive statistics and PK analysis.
- In the event that two BLQ values are followed by a value within the quantification limit, the quantifiable value may be excluded from the analysis.

PK Parameter Estimation:

The PK parameters will be estimated by non-compartmental analysis (NCA) using Phoenix WinNonlin (v8.3 or later) using the data imputations described above. Actual sampling time points relative to dosing will be used for the NCA. There will be no imputation for missing data. No formal "outlier" analysis is planned. A profile must include at least consecutive quantifiable concentrations to be included in PK analysis. Subject profiles that are excluded from PK analysis (e.g. missing more than 2 samples, etc.) will be included in the concentration tables only and the reason for exclusion will be provided in the PK report.

Peak plasma concentrations (C_{max}) post dose administration and the corresponding T_{max} will be determined by direct assessment (no calculations) of the concentration vs time data.

All AUC calculations will be performed using the linear trapezoidal rule.

If the data permit, the terminal rate constant (λz) will be calculated. The value of λz will be determined by the slope of the regression line of the natural log transformed concentrations vs time with the following constraints:

1. At least 3 data points post the C_{max} should be used in the regression; and
2. The correlation coefficient (R^2) of regression should be > 0.80 .

To optimize the reliability of the identified terminal phase (λz), where possible, the data points used to define the λz will be manually selected. The λz profiles that do not meet the guidelines stated above will not report the AUC_{INF} , $t_{1/2}$, CL or Vz parameters for that subject profile.

When possible, AUC_{INF} will be calculated as: $AUC_{last} + (C_{last} / \lambda z)$. CL will be calculated as: $Dose / (AUC_{INF})$ and Vz will be calculated as: $Dose / (AUC_{INF} * \lambda z)$. Terminal half-life ($t_{1/2}$) will be calculated as: $\log_e(2) / \lambda z$. If the lambda z range is not at least 2-fold greater than the calculated half-life value, the half-life value will be flagged and excluded from summary descriptive statistics.

If there any deviations from the planned treatment, then the analysis model specified or methods of analysis may be re-evaluated, as appropriate. Details of any deviations from the planned analysis will be documented in the PK report.

Individual subject PK parameters will be listed and summarized by cohort / dose levels with descriptive statistics (e.g. N, arithmetic mean, SD, median, minimum, maximum, geometric mean and CV%).

Individual parameters and descriptive statistics will be presented to 3 significant figures, except N, which will be reported as whole number, while individual T_{max} and half-life values will be reported to two significant figures.

PK Figures:

Mean \pm SD Concentration vs nominal time profiles will be generated on log/linear scales by cohort.

Overlay plots of all individual plasma concentration by actual time (or nominal time) for each cohort will be generated on log/linear axis, with each subject data represented with a different symbol and included in a legend. Individual subject concentration by time plots will also be produced on log/linear axis.

Mean \pm SD AUC_{last} versus dose plots will also be generated to assess dose proportionality / linearity.

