1.3 SCHEDULE OF ACTIVITIES (SoA)

Table 1 Schedule of Activities (Subjects with Neurodegenerative Diseases, All Dose Cohorts)

Study Procedures	Screening ¹	Treatment	Follow-up	Notes
Study Visit	-42 to -1	Day 1	Day 8/EOS/ET	
Visit window (days)	42		+2	
Informed consent	X			
Domiciled		X ^a		a. Subjects will be admitted to the clinical research unit in the morning for 8 hours confinement
Medical/ocular history/Physical exam	X			On Day 1, PE may be repeated if abnormalities are detected at screening. Relevant ocular and disease-specific history will be captured up to date of diagnosis.
Eligibility (inclusion/exclusion criteria)	X			
Body weight and Height	X			
Eye examination/	X	X	X	Refer to Section 8.1.1.
Color fundus photography	X			
Vital signs	X	X ^b	X	b. To be collected predose, and at 0.25, 0.5, 1, 2, 8 hours postdose. A window of \pm 5 minutes will be allowed for measurements up to 2 hours, and \pm 10 minutes beyond 2 hours.
12-lead safety (ECG)	X	X ^c	X	c. Triplicate at the following timepoints: predose (within 1 hour), and at 90 minutes (\pm 15 minutes) and 8 hours (\pm 60 minutes) postdose or before discharge
Safety laboratories	X	X ^d	X	Refer to Section 10.2. d. To be collected predose on Day 1 and before discharge
Urinalysis	X	X	X	
Pregnancy test	S	U (predose)	U	S = Serum; U = Urine
Adverse event reporting	X	X	X	

Study Procedures	Screening ¹	Treatment	Follow-up	Notes
Study Visit	-42 to -1	Day 1	Day 8/EOS/ET	
Visit window (days)	42		+2	
Concomitant medications	X	X	X	
Retinal fundus fluorescence (FF) imaging		X ^e	X	e. Refer to Section 8.1.2
Retinal optical coherence tomography (OCT) and OCT angiography (OCTA)	X		X	
Blood PK sampling		X ^f		f. On Day 1, PK blood samples will be collected at the following time points: 0 (predose), and at 3, 6, 15, and 30 minutes postdose and 1, 2, 4, 6, and 8 hours postdose. A window of ± 5 minutes will be allowed for samples collected from 30 minutes to 2 hours, and ± 10 minutes beyond 2 hours.
Study drug administration		X		

Abbreviations: AE, adverse events; ECG, electrocardiogram; EOS, end of study; ET, early termination; FU, follow-up; PE, physical examination; PK, pharmacokinetics.

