6 STUDY DRUG

6.1 STUDY DRUG(S) ADMINISTRATION

6.1.1 Study Drug Description

AMDX-2011P, a retinal tracer (small molecule), is a phosphate prodrug hydrolyzed in vivo to the pharmacologically active molecule AMDX-2011.

	Active
Study Drug Name (INN)	AMDX-2011P
Type	Retinal tracer (small molecule)
Dose Formulation	Solution for injection
Unit Dose Strength(s)	mg
Dosage Level(s)	
 • Cohort 1 – 25 mg (1 mL) • Cohort 2 – 50 mg (2 mL) • Cohort 3 – tentative 100 mg (4 mL) • Cohort 4 – tentative 150 or 200 mg (6-8 mL) 
For Cohorts 3-4, doses to be confirmed by SMC based on emerging data from prior cohorts. Intermediate and/or higher dose levels may be explored.

Route of Administration	IV bolus injection over 2 minutes
Use	Experimental
Sourcing	The drug product is manufactured by Pace (Salem, NH), and provided centrally by the Sponsor or subsidiary, or designee.
Preparation	Individual doses of AMDX-2011P will be prepared by pharmacy staff and will be provided to study personnel for administration. Procedures relating to study drug preparation will be outlined in the Pharmacy Manual. AMDX-2011P will be provided frozen (at -20°C) in a 10 mL amber vial containing 5.5 mL of solution at a concentration of 25 mg/mL. It is a single dose vial. Vials must not be shared between subjects. The solution is light sensitive and must be protected from light at all times. AMDX-2011P must be thawed to room temperature prior to administration; once thawed, it must be used within 3 hours.
Post administration instructions	Subjects to be instructed to avoid direct sun and wearing light protective eye gear such as sunglasses for 24 hours after the dose. Subjects will be evaluated for signs and symptoms of phototoxicity.
Packaging and Labeling	The study drug will be dispensed in single administration vials. Study drug will be labeled as required per local regulations. All packaging and labeling operations for the study drug will be performed according to

	Active
	current Good Manufacturing Practices and the relevant regulatory requirements.
Storage Condition	Study drug is to be stored in a secure freezer (-20°C) and monitored (manual or automated) in accordance with the labeled storage conditions with access limited to the investigator and authorized site staff.

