4.3 Pharmacokinetic (PK) Population

The Pharmacokinetic (PK) Population includes all enrolled subjects who receive any amount of study drug and who have at least one post-baseline PK measurable samples.

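### SAP 6.9 names a count of missing samples as a ground for dropping a subject's whole PK profile, without regard to which samples are missing

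*SAP*

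**What the plan says.** Protocol 1.3 (Table 1, note f) schedules PK blood at "0 (predose), and at 3, 6, 15, and 30 minutes postdose and 1, 2, 4, 6, and 8 hours postdose": one predose and nine postdose samples. Dosing is an "IV bolus injection over 2 minutes" (Protocol 6.1.1). Under SAP 6.9, Cmax and Tmax "will be determined by direct assessment (no calculations) of the concentration vs time data", and AUC uses the linear trapezoidal rule.

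On exclusion from non-compartmental analysis, SAP 6.9 says: "Subject profiles that are excluded from PK analysis (e.g. missing more than 2 samples, etc.) will be included in the concentration tables only". It adds that "the reason for exclusion will be provided in the PK report". The sentence before it reads "A profile must include at least consecutive quantifiable concentrations to be included in PK analysis"; in the text available to me no number stands there. That may be a loss in reading the PDF, and I do not count it against the plan.

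Three other provisions bear on the point:

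- SAP 4.3 admits to the PK Population subjects "who have at least one post-baseline PK measurable samples".
- SAP 6.9 has a BLQ value after Cmax "treated as a non-numerical value and excluded from descriptive statistics and PK analysis".
- Where the terminal slope fails its criteria, SAP 6.9 withholds only the parameters that depend on it (AUCinf, half-life, CL and Vz), not the whole profile.

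**The concern.** After a two-minute injection the parent's peak should fall at the first samples. Cmax and Tmax therefore depend on those samples, the terminal slope on the late ones, and AUC on both in proportions set by the half-life. A count treats all nine alike. It can remove a subject whose peak is fully observed, and it is silent on one whose peak was never sampled.

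Early losses are plausible. Protocol Table 5 puts imaging at 0–1, 2 and 5 min, and Protocol Section 8 puts blood draws last where procedures coincide, subject to the PK windows.

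PK parameters are a secondary endpoint, and the SAP plots AUClast against dose to assess proportionality. Protocol 10.1.5 lists PK among the data the SMC may use. Cohorts 1 and 2 may hold as few as three subjects, so one profile can be a third of a dose level.

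**Working it through.** The plan gives no figure that rests on this rule, so there is none to reproduce. The check asks what the count does on the study's own schedule.

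**1. Patterns (postdose samples only).** Missing exactly three of nine: C(9,3) = 84 ways. Both the 3 and 6 min samples are present in C(7,3) = 35 of these (42%), and all 35 meet the ground. Missing exactly two: C(9,2) = 36 ways. One of these, 3 and 6 min, removes both earliest samples and does not meet the ground. These are counts of patterns, not probabilities.

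**2. Half-life implied by Protocol Table 4 (25 mg row).** Assume mono-exponential decline, so k = Cmax/AUC and half-life = ln 2 × AUC/Cmax.

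- AMDX-2011P: 49.0/135 = 0.363 h; half-life 0.252 h (15.1 min).
- AMDX-2011: 19.1/43.8 = 0.436 h; half-life 0.302 h (18.1 min).

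The 50, 100, 150 and 200 mg rows give 0.247–0.252 h and 0.303 h.

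**3. Samples at 4, 6 and 8 h missing (meets the ground).** Cmax and Tmax do not change. For AUClast, apply the linear trapezoid to C(t) = C0 × exp(−kt), starting from back-extrapolated C0 and treating all full-profile samples as quantifiable. Areas are in units of C0 × h.

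| Half-life | Area 0–2 h | Area 2–8 h | AUClast without late samples / full |
|---|---|---|---|
| 0.25 h | 0.3869 | 0.0039 | 99.0% |
| 0.30 h | 0.4586 | 0.0100 | 97.9% |
| 0.5 h | 0.7064 | 0.0708 | 90.9% |
| 1 h | 1.0999 | 0.4102 | 72.8% |

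At 2 h the ratio is 52.5%.

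**4. Samples at 3 and 6 min missing (does not meet the ground).** The largest remaining value is at 15 min, so observed Cmax relative to the 3 min value is exp(−k × 12/60).

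- Projected parent half-life: exp(−2.755 × 0.2) = 0.58, about 42% too low.
- 30 min: exp(−1.386 × 0.2) = 0.758, 24% too low.
- 1 h: exp(−0.693 × 0.2) = 0.871, 13% too low.

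Tmax would be reported as 15 min. The same sum for AMDX-2011 gives 0.63, but it ignores formation of the metabolite, so I do not rely on it.

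**5. C0 and parent AUC in that same profile.** On a mono-exponential curve, log-linear back-extrapolation from 15 and 30 min returns the same C0. At 0.25 h the 0–15 min trapezoid becomes (1 + 0.5)/2 × 0.25 = 0.1875 instead of 0.1818. Full-profile AUC is 0.3908, so the ratio is 0.3965/0.3908 = 1.015. The harm shown is to observed Cmax and Tmax, not to C0 or parent AUC.

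**The case against.** The strongest reply is that the count is an illustration in an open list. The SAP does not say that exclusion is automatic whichever samples are missing, and it does not say that a profile missing two or fewer is kept. A reader might infer both. The first is the natural reading, since the count is named as a ground and no timing is mentioned, but the second comes only from silence. The neighbouring criterion on consecutive quantifiable values might also act on such a profile. This stands, and limits the claim to what the named ground does.

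The AUC argument depends on a projection. Table 4 is scaled from dog data, and one-compartment decline is my assumption. At a half-life of 1 h or more, withholding AUC from a profile that stops at 2 h would be defensible. That stands for AUC. It does not justify removing Cmax and Tmax.

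A reader might infer that the rule overrides the PK Population. It does not: SAP 4.3 defines a population and SAP 6.9 applies a narrower step within it. The two are simply not reconciled.

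A reader might also infer that late BLQ results count as missing and so could empty whole cohorts. The SAP treats BLQ and missing data separately, and neither document gives a quantification limit, so this is not supported. It is a gap that one sentence would close.

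Finally, all scheduled PK samples fall within a supervised eight-hour stay, no rate of missing samples is given, the analysis is descriptive, and Protocol 4.1 rests escalation on safety and tolerability. These points limit how often the rule would matter and with what effect.

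**Conclusion.** The concern holds in this form: the one quantified example of a ground for exclusion ignores timing and acts on the whole profile, so it does worse than the parameter-level handling SAP 6.9 already uses for the terminal slope. It would cost a subject without the 4, 6 and 8 h samples an unaffected Cmax and Tmax, and an AUClast about 98–99% complete at the projected half-lives (91% at 0.5 h, 73% at 1 h). It does not reach a profile without the 3 and 6 min samples, whose observed parent Cmax would be about 42% too low (24% at 30 min, 13% at 1 h). No other stated rule clearly withholds that value, though its retention is inferred.

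These sizes assume mono-exponential decline, projected rather than observed PK, and nominal sampling times. How often either pattern will occur is unknown. Because the list is open and reasons are given in the PK report, exclusions could be settled after concentrations are seen. Closing the list before database lock is worth doing.

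**What to change.** In SAP 6.9, replace the whole-profile count with a closed set of evaluability rules by parameter:

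- **Cmax and Tmax:** list them, but leave them out of summaries, when both the 3 and 6 min samples are missing. Requiring both samples would go too far, because it would discard a peak seen at 3 min when only the 6 min sample was lost.
- **Late samples:** their absence should not remove Cmax, Tmax or C0.
- **AUClast:** report it when early coverage is adequate, with adequate defined in advance. Flag it when sampling stopped while the concentration was still quantifiable and a material part of the AUC may lie beyond the last sample.
- **Terminal-slope parameters:** keep the existing criteria.
- **BLQ and predose:** state that a BLQ result is an obtained sample, and whether a missing predose sample counts.
- **Link to SAP 4.3:** say that the PK Population governs who is listed and the parameter rules govern who is summarised.
- **Tables:** print N for each parameter.

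The cost is SAP wording and minor programming, with no new data. The downside is that N will differ between parameters within a cohort. A peak read at 6 min when only the 3 min sample is missing would still be summarised; at the projected parent half-life it is about 13% low (exp(−2.755 × 0.05) = 0.87).

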6.4 STUDY DRUG COMPLIANCE

Study drug will be administered at the study site by the investigator or designee, as per the SoA (Section 1.3).

A record of the dose of AMDX-2011P administered to each subject must be maintained and reconciled with study drug and compliance records. Study drug start time will also be recorded in the electronic case report form (eCRF).

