8.3 PHARMACOKINETIC ASSESSMENT

Blood samples for determination of plasma concentrations of AMDX-2011P and AMDX-2011 will be collected as detailed in the SoA (Section 1.3). The timings of sample collection may be amended during the study conduct on the basis of emerging data to allow optimal characterization of the PK profile of AMDX-2011P and AMDX-2011.

Plasma concentrations of AMDX-2011P and AMDX-2011 will be measured by a specific and validated liquid chromatography-tandem mass spectroscopy (LC-MS/MS) method.

The following pharmacokinetic parameters (where appropriate) will be calculated by noncompartmental analysis from plasma concentrations of AMDX-2011P and for AMDX-2011 as defined in [Table 6](#).

Table 6 Pharmacokinetic Parameters

Parameter	Definition
C ₀	Back-extrapolated concentration at time = 0 hr (AMDX-2011P only)
C _{max}	Maximum observed drug concentration
T _{max}	Time of the maximum drug concentration
AUC _{0-last}	Area under the drug concentration-time curve from time zero to the last measurable concentration
AUC _(inf)	Area under the drug concentration-time curve from time zero to infinity
AUC _(0-t)	Area under the drug concentration-time curve from time zero to time t
t _{1/2}	Apparent terminal half-life
λ _Z	Apparent terminal elimination rate constant
CL	Systemic clearance (AMDX-2011P only)

Parameter	Definition
V _{ss}	Steady-state volume of distribution (AMDX-2011P only)

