5.3 Pharmacokinetic Endpoints

The following PK parameters will, where possible, be determined (to a precision minimum of 3 significant figures):

Parameter	Definition
C_0 (ng/mL)	Extrapolated concentration at time equal to zero
C_{max} (ng/mL)	Maximum observed drug concentration
T_{max} (hr)	Time of the maximum drug concentration

Parameter	Definition
AUC _{0-last} (hr*ng/mL)	Area under the drug concentration-time curve (AUC) from time zero to the last measurable concentration.
AUC _{INF} (hr*ng/mL)	AUC from zero extrapolated to infinity
AUC _(0-t)	AUC from time zero to time t
CL/F (L)	Apparent total body clearance following IV administration
t _{1/2} (hr)	Apparent terminal half-life
λz (1/hr)	Apparent terminal elimination rate constant
V _{ss} (L)	Steady-state volume of distribution

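### The linear trapezoidal rule applied to every AUC inflates prodrug AUC after a 2-minute IV dose, by about 5–8% from the rule alone, and the SAP leaves the time-zero value and the dose input unstated

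*SAP*

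**What the plan says.** SAP section 6.9 fixes one integration rule for both analytes: "All AUC calculations will be performed using the linear trapezoidal rule". It makes no exception for the declining limb.

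Protocol section 6.1.1 gives the dose as an "IV bolus injection over 2 minutes". The Schedule of Activities (protocol section 1.3) sets PK samples at "0 (predose), and at 3, 6, 15, and 30 minutes postdose and 1, 2, 4, 6, and 8 hours postdose".

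C0 is a reported parameter. The protocol (section 8.3, Table 6) defines it as "Back-extrapolated concentration at time = 0 hr (AMDX-2011P only"). SAP section 5.3 lists it as "Extrapolated concentration at time equal to zero", without limiting it to the prodrug.

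On timing, SAP section 6.9 says "Actual sampling time points relative to dosing will be used for the NCA" but does not say whether the clock starts at the beginning or the end of the injection. Protocol section 6.4 says "Study drug start time will also be recorded in the electronic case report form (eCRF"). SAP section 6.9 sets values below the quantification limit to zero when they precede Cmax. Neither document says which value opens the AUC at time zero, or whether the dose enters the noncompartmental analysis as instantaneous or as a 2-minute input.

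**The concern.** After an IV dose the plasma curve falls roughly exponentially. The linear rule is accurate when samples are close together relative to the half-life and overstates area when they are not. Here the samples become sparse after 30 minutes, while the half-life implied by the sponsor's own projection is about a quarter of an hour.

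The 2-minute injection raises a second issue. The first sample is at 3 minutes, so the area before it depends on what is assumed at time zero, and the SAP does not say.

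The PK parameters are a secondary endpoint. Clearance is calculated as dose divided by AUCinf, so any inflation of AUC lowers clearance directly. AUClast is also plotted against dose to look at proportionality, and under protocol section 10.1.5 the safety committee may look at PK when it authorizes escalation.

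**Working it through.** The documents give no figure for AUC error, so there is none to reproduce. The check applies the planned calculation to a curve built from Table 4.

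**Inputs from the documents.** Table 4 (protocol section 4.3), AMDX-2011P: 25 mg, AUC 49.0 h·ng/mL and Cmax 135 ng/mL; 200 mg, AUC 383 and Cmax 1070. Injection time 2 minutes. Sampling times as in the Schedule of Activities.

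**Assumptions.** Mono-exponential decline; Table 4 Cmax taken as the concentration after an instantaneous dose. The lower limit of quantification (LLOQ) is not given; 0.1 to 5 ng/mL was tried.

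**Step 1: half-life.** k = Cmax/AUC = 135/49.0 = 2.755 per hour, so t½ = 0.693/2.755 = 0.252 h, about 15.1 minutes. At 200 mg, k = 1070/383 = 2.794 per hour and t½ is about 14.9 minutes. The 30–60 minute gap is therefore about 2 half-lives and the 1–2 hour gap about 4.

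**Step 2: the rule alone, instantaneous dose, 25 mg.** As a share of AUCinf, the true area from a to b is exp(−ka) − exp(−kb). The linear area is k(b − a)[exp(−ka) + exp(−kb)]/2.

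- 30–60 min: true 0.2522 − 0.0636 = 0.1886; linear 2.755 × 0.5 × (0.2522 + 0.0636)/2 = 0.2175; excess 0.0289.
- 1–2 h: true 0.0636 − 0.0040 = 0.0596; linear 2.755 × 1 × (0.0636 + 0.0040)/2, about 0.093; excess about 0.034. The interval is about 56% too high but holds only about 6% of the AUC.
- The four intervals before 30 min add 0.0002 + 0.0002 + 0.0036 + 0.0098 = 0.0138.

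With the last measurable sample at 1 h, the error in AUClast is (0.0138 + 0.0289)/0.936 = +4.6%. With it at 2 h, it is about 0.076/0.996 = +7.7%.

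**Step 3: the first 3 minutes with a 2-minute input, 25 mg, clock at injection start.** The true area from 0 to 3 minutes is 8.7% of AUCinf. A line from a back-extrapolated C0 gives 13.5%, an excess of about 4.8 points. A line from the predose zero gives 6.3%, a shortfall of about 2.5 points. The back-extrapolated C0 exceeds the concentration at the end of injection by exp(2.755 × 2/60) = 1.096, about 10%.

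**Step 4: combined error in prodrug AUClast.**

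| Handling | 25 mg, last sample 1 h / 2 h | 200 mg, last sample 1 h / 2 h |
|---|---|---|
| Instantaneous dose, linear | +4.6% / +7.7% | +4.6% / +7.7% |
| 2-min input, start clock, C0 in AUC, linear | +9.9% / +12.8% | +10.0% / +12.9% |
| 2-min input, start clock, predose zero, linear | +2.1% / +5.5% | +2.2% / +5.6% |
| 2-min input, end-of-injection clock, C0 in AUC, linear | −0.4% / +2.9% | −0.4% / +2.8% |
| Start clock, C0 in AUC, linear-up/log-down | +5.1% / +4.8% | +5.1% / +4.8% |
| Start clock, predose zero, linear-up/log-down | −2.6% / −2.5% | −2.7% / −2.5% |

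Bi-exponential prodrug curves with C0 in the AUC and the linear rule gave +10.6% to +13.5% at LLOQ 0.1–1 ng/mL and up to +17% at 5 ng/mL. AUCinf could turn negative in error where the tail was cut off.

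**Step 5: clearance.** From the rule alone, AUCinf is +4.3% to +7.7%, so CL is 1 − 1/1.043 = 4.1% to 1 − 1/1.077 = 7.1% too low. With C0 in the AUC, AUCinf is +9.2% to +12.9% and CL is about 8% to 11% too low.

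**Step 6: dose.** At a common last time the 25 mg and 200 mg errors agree to about 0.1 point. Projected prodrug concentrations at 2 h are 0.57 ng/mL at 25 mg, 1.15 at 50 mg and 4.2 at 200 mg. An LLOQ of 1 ng/mL would end the 25 mg profile at 1 h and the others at 2 h, opening a gap of about 3 points (9.9% against 12.9% with C0 in the AUC). An LLOQ of 0.1 ends every dose at 2 h, and an LLOQ of 5 ends every dose at 1 h.

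**Step 7: AMDX-2011.** This is formed from the prodrug, so it was modelled with a formation phase (Tmax 2.5–6 minutes, assumed). The linear rule gives +0.3% to +8.1% with a start clock and −8.9% to +3.4% with an end clock. Linear-up/log-down with a start clock gives −0.3% to −1.9%.

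**The case against.** The sponsor can fairly say that the linear rule is prespecified, that PK is descriptive with no tests, and that no AUC threshold governs any decision. All concentrations and actual sampling times will be listed, so AUC can be recomputed under any rule. All of that stands and limits the weight of the point. It does not make the linear rule the better choice for this curve and these sampling times.

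Four stronger readings are tempting and are not supported.

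- **C0 opens the AUC as if the dose were instantaneous, so exposure is overstated by 10% or more.** Neither document says so. C0 is only a listed parameter, and the rule that sets early unquantifiable values to zero fits a predose-zero start equally well. Nor does recording the start time rule out recording the end time.
- **Both analytes are overstated.** The protocol limits C0 to the prodrug, and a formed metabolite can be understated.
- **The error differs by dose and distorts the proportionality plot.** Table 4 is dose-linear and the injection time is fixed. Divergence needs an LLOQ that truncates the low doses earlier, and no LLOQ is given.
- **The error could mask the margin between projected prodrug AUC at 200 mg (383) and the male-dog no-effect value (400).** That gap is 17/383 = 4.4%, similar in size to the error, but 383 is a projection and the documents attach no rule to measured AUC.

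**Conclusion.** The concern holds in a limited form. The linear rule itself inflates prodrug AUClast by about 5–8% and lowers clearance by about 4–7%, given mono-exponential decline at the Table 4 rate and a last measurable sample at 1 or 2 hours. The net error under the actual 2-minute injection cannot be fixed from the documents: it runs from about −0.4% to +13% for the prodrug, depending on the time-zero value and the clock, and has either sign for AMDX-2011. That range is itself the reason to specify these settings. Dose-dependence is conditional on the LLOQ and should not be asserted. No safety or imaging conclusion depends on it.

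**What to change.** In SAP section 6.9:

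1. Replace the linear rule with linear-up/log-down for all AUCs.
2. Run the AMDX-2011P analysis as a 2-minute infusion, with the clock at injection start, and state the time-zero value (for example, the predose value set to zero).
3. In section 5.3, restrict C0 to AMDX-2011P as the protocol does, label it an extrapolated value, and keep it out of the AUC.

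Changing the rule without the third item leaves about +5% if C0 enters the AUC. The full change does not give zero error: about −2.5% remains for the prodrug in the mono-exponential case, from the 0–3 minute interval.

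The cost is a few SAP sentences and standard software settings. The nominal 2 minutes is enough for the infusion input; one case report form field for the end time would allow actual durations. Reported AUC becomes slightly smaller than under the linear rule.

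### SAP 6.9 gives a formula and a failed-slope rule for Vz, which is not a listed endpoint, and gives neither for the listed volume endpoint, Vss.

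*SAP*

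**What the plan says.** **Listed endpoint.** SAP 5.3 lists "Steady-state volume of distribution" and no other volume. Protocol section 8.3, Table 6, lists the same parameter and restricts it to AMDX-2011P. Vz is in neither list, and SAP 1.1 (changes from protocol) records only a wider visit window.

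**Formulas.** SAP 6.9 writes out AUCinf = AUClast + Clast/λz, CL = Dose/AUCinf and t1/2 = ln 2/λz. For volume, the text is "and Vz will be calculated as" Dose/(AUCinf × λz). It gives no expression for Vss or for mean residence time (MRT).

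**Failed-slope rule.** The slope needs "At least 3 data points post the" Cmax and an R² above 0.80. Then: "profiles that do not meet the guidelines stated above will not report the" AUCinf, t1/2, CL or Vz. Vss is not named.

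**Span rule.** This comes later and has a narrower consequence: "If the lambda z range is not at least 2-fold greater than the calculated half-life value", then "the half-life value will be flagged and excluded from summary descriptive statistics". SAP 6.9 otherwise says that individual PK parameters are listed and summarized by cohort and dose level.

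**The concern.** PK parameters are a secondary endpoint of a first-in-human study, and the descriptive summaries are the whole result. A programmer following SAP 6.9 has instructions for a volume nobody listed and none for the one that was listed. Two things can follow. Vz may be tabulated where Vss was intended. Or Vss may be taken from the software output and reported for profiles whose slope the SAP has rejected, because the rule that withholds the other slope-derived parameters does not mention it.

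The span rule raises a lesser question. A slope judged too short to summarize a half-life still feeds Vz, which divides by the same λz. And because the exclusion depends on the estimated half-life, it takes out the longest ones.

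**Working it through.** **1. Do Vz and Vss differ?** For a bi-exponential profile after an IV bolus, with terminal rate b:

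- Vz = CL/b
- Vss = CL × MRT, with MRT = AUMC/AUC = (1 − s)/a + s/b, where s is the share of AUC in the terminal phase

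MRT is a weighted average of 1/a and 1/b, so it is below 1/b whenever there are two phases. Vz therefore exceeds Vss, and the two are equal only for a single phase.

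From protocol Table 4, the projected AMDX-2011P AUC at 25 mg is 49.0 hr·ng/mL, so CL = 25 mg/49.0 = 510 L/h. The half-lives and shares are assumptions, because the documents give no human terminal half-life. With an initial half-life of 0.15 h and a terminal half-life of 3 h, Vz = 510.2 × 3/0.693 = 2208 L.

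| Terminal share of AUC | MRT (h) | Vss (L) | Vz/Vss |
|---|---|---|---|
| 10% | 0.628 | 320 | 6.9 |
| 30% | 1.450 | 740 | 3.0 |
| 60% | 2.683 | 1369 | 1.6 |

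A second set of assumptions (fast half-life 0.2 h, slow 1–4 h, 1–20% of C0 in the slow phase) gives ratios from 1.19 (20%, 4 h) to 5.48 (1%, 2 h). Taken together, the range is about 1.2 to 7.

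**2. Does Vss need the slope?** Yes. AUMCinf = AUMClast + tlast × Clast/λz + Clast/λz². In the 30% row, with the last sample at 8 h:

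- AUC beyond 8 h: 0.3 × 2^(−8/3) = 4.7% of the total.
- AUMC beyond 8 h: 0.0472 × (8 + 4.33)/1.450 = 40% of the total.
- With a terminal half-life of 1 h instead, the two shares are 0.1% and 2%.

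So when the terminal phase is slow, Vss leans on the slope far more than AUCinf does, yet AUCinf is withheld and Vss is not.

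How often R² would fail also depends on assumptions. With a slope fitted to 4, 6 and 8 h, 30% terminal share and 15–25% concentration noise, simulated failure rates were about 0% at a true half-life of 1 h, 0.4–8% at 2 h and 5–24% at 3 h.

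**3. Injection time.** Protocol section 6.1.1 specifies a bolus over 2 minutes, so the MRT correction is 1 minute. It is worth 510/60 = 8.5 L, or 2.7% of a Vss of 320 L and 0.6% of 1369 L.

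**4. Span rule (conditional).** Samples are taken at 3, 6, 15 and 30 min and at 1, 2, 4, 6 and 8 h. A fit over 2–8 h (6 h) excludes half-lives above 3 h; over 4–8 h (4 h), above 2 h; over 1–8 h (7 h), above 3.5 h.

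For lognormal half-lives with an assumed CV of 40% (σ = √ln 1.16 = 0.385) and z = ln(cut-off/median)/σ, the fraction excluded is 1 − Φ(z), and the mean of those kept is Φ(z − σ)/Φ(z) times the full mean.

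| Median t1/2 | Window | Excluded | Mean too short by |
|---|---|---|---|
| 1 h | 2–8 h | about 0% | about 0% |
| 2 h | 2–8 h | 15% | 12% |
| 3 h | 2–8 h | 50% | 30% |
| 4 h | 2–8 h | 77% | 43% |
| 0.3 h | 15 min–1 h (later samples BLQ) | 28% | 20% |

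The only decline the documents imply is ln 2 × AUC/Cmax from Table 4: 0.693 × 49.0/135 h = 15 min for AMDX-2011P and 0.693 × 19.1/43.8 h = 18 min for AMDX-2011. That is not a terminal half-life, but it gives no support for 2–4 h.

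In the simulation of step 2 at a true 3 h, profiles that passed R² but failed span had a 5th–95th percentile Vz of 1520–3115 L (15% noise) or 1389–3872 L (25% noise), against a true 2208 L. Their extrapolated AUC was only about 2–10%. In that scenario Vz is affected clearly, and AUCinf and CL little.

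**The case against.** A reader might infer that the trial will report the wrong volume. The documents do not go that far. SAP 5.3 still says its listed parameters, Vss among them, will be determined where possible. Standard noncompartmental software produces Vss, and C0 also lacks a formula in SAP 6.9 without anyone concluding that it is dropped. This stands: the finding is a missing definition and an incomplete withholding rule, and the ratio in step 1 matters only if Vz is presented as Vss. It does not rescue the withholding rule. One can argue that withholding CL implies withholding Vss, but the SAP names parameters one by one and does not say so.

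A second tempting inference is that the summarized half-life is biased short and that CL and AUCinf are unreliable. Every sizeable half-life bias above needs an assumed half-life of 2 h or more, or early BLQ. The SAP fixes no fitting window, because points are chosen manually. Slopes that fail the point or R² criterion already lose AUCinf and CL. Flagged half-lives leave only the summary statistics; individual values are still listed, and N by dose is planned. The dose-proportionality plot uses AUClast, which does not depend on λz.

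Third, it is tempting to extend the span exclusion to AUCinf, CL and Vss and to cap extrapolated AUC at 20%. That would carry the same selection on half-life into those summaries, in cohorts planned at 3–12 subjects. The 20% figure is a convention that the documents do not contain.

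**Conclusion.** SAP 6.9 is wrong as written on the volume parameter. The formula and the withholding rule refer to Vz, the endpoint is Vss, and no change from protocol is declared. That much follows from the text alone. The size, Vz at about 1.2 to 7 times Vss, rests on assumed bi-exponential profiles. If the decline were truly single-phase, the two volumes would coincide.

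The span-rule point is secondary and conditional. It is an inconsistency in the text, because Vz stays in the summaries when the half-life from the same slope is removed. It has practical weight only with a terminal half-life of about 2 h or more, or with BLQ late samples. The documents establish neither, so bias in the half-life and unreliability of CL or AUCinf should not be stated as findings.

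The endpoint is secondary and descriptive, with no formal tests. The correction is nearly free and should be made before database lock.

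**What to change.** In SAP 6.9:

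1. Define Vss = CL × MRTinf for AMDX-2011P only, as in protocol Table 6, with MRTinf = AUMCinf/AUCinf minus half the 2-minute injection time. State the same analyte restriction in SAP 5.3.
2. Add Vss to the parameters withheld when the slope has fewer than 3 points after Cmax or R² is not above 0.80.
3. Either delete Vz or list it in SAP 5.3 as a separate, separately named parameter, and record the addition in SAP 1.1.
4. For span failures, flag the other λz-derived parameters (AUCinf, CL, Vss and Vz if kept) in the same profiles. Report the number flagged by dose, and show the median half-life with and without flagged values. Excluding AUCinf and CL, or setting an extrapolation limit, is not needed.

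The cost is a few lines of SAP text and a flag column in the PK tables. Sampling, conduct and the protocol do not change.
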